8.1 Efficacy Assessments

8.1.1 Primary/Secondary Variable: Urinary Albumin to Creatinine Ratio (UACR)

The UACR is a key marker for assessing kidney function. The UACR is a ratio between 2 measured substances (urine albumin and creatinine), which estimates 24-hour urine albumin excretion.

The UACR is calculated as follows:

- $\text{UACR (mg/g)} = \text{urine albumin (mg/dL)} / \text{urine creatinine (g/dL)}$

Urine samples for the determination of albumin and creatinine levels and calculation of UACR will be collected at the time points described in the SoA (Table 1):

- At screening, containers to collect the urine samples will be dispensed to the participants. A spot urine from first morning void will be collected the next day and analysed centrally.
- For subsequent visits, containers to collect the urine samples will be dispensed to the participants. Participants will collect first morning void urine samples at home on 3 consecutive days (ideally day of visit and preceding 2 days [refrigerated overnight] which will be returned on the day of visit). Samples will be analysed centrally.
Note: The samples collected on visit days will also be used for the determination of exploratory urinary parameters (see Section 8.5.3.1).
- At each visit (except for screening), the geometric mean of the triplicate UACRs will be computed and used for all analysis of UACR.

8.1.2 Other Secondary Variables

8.1.2.1 Office/Clinic Blood Pressure Measurement

Blood pressure measurements for participants who receive dapagliflozin monotherapy or different doses of zibotentan combined with dapagliflozin 10 mg will be done during clinic visits at the time points for vital signs indicated in the SoA (Table 1 and Section 8.2.2).

8.1.2.2 Serum Analysis of Creatinine and Cystatin C (eGFR)

Estimated GFR is another measure that is considered as a standard for assessment of kidney function. Estimated GFR is calculated based on serum creatinine values using the widely validated and accepted CKD-EPI equation. Blood samples for estimation of serum creatinine (clinical chemistry) are collected at various time points during the course of the study as shown in the SoA (Table 1).

Estimated GFR, using serum creatinine, is calculated as follows:

- $eGFR \text{ (mL/min/1.73 m}^2\text{)} = 141 \times \min(\text{SCr}/\kappa, 1)^\alpha \times \max(\text{SCr}/\kappa, 1)^{-0.209} \times 0.993 \text{ Age} \times (1.018 \text{ if female}) \times (1.159 \text{ if Black})$

Where SCr = serum creatinine (in mg/dL), κ is 0.7 for females and 0.9 for males, α is -0.329 for females and -0.411 for males, min indicates the minimum of SCr/ κ or 1, and max indicates the maximum of SCr/ κ or 1.

Alternatively, serum cystatin C provides GFR estimates that are nearly as accurate as serum creatinine adjusted for age, sex, and race thus providing an alternative GFR estimate that is not linked to muscle mass (Scholtes et al, 2020, Stevens et al, 2008). Blood samples will be collected for measurement of cystatin C, at specified time points in the SoA (Table 1).

Estimated GFR, using cystatin C, is calculated as follows:

- $eGFR = 133 \times \min(\text{S}_{\text{cys}}/0.8, 1)^{-0.499} \times \max(\text{S}_{\text{cys}}/0.8, 1)^{-1.328} \times 0.996^{\text{Age}} \times 0.932 \text{ [if female]}$

Where S_{cys} is standardised serum cystatin C (in mg/L), min indicates the minimum of $\text{S}_{\text{cys}}/0.8$ or 1, max indicates the maximum of $\text{S}_{\text{cys}}/0.8$ or 1, and age = years.

Estimated GFR calculations using the CKD-EPI formulae (in both ways, based on cystatin C and based on creatinine) will be performed by the central laboratory.

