5.1 Inclusion Criteria

Participants are eligible to be included in the study only if all of the following criteria apply:

Age

- 1 Participant must be 18 years of age or older at the time of signing the informed consent.

Type of Participant and Disease Characteristics / Laboratory Parameters

- 2 Diagnosis of CKD, defined as:
 - (a) eGFR (CKD-EPI) ≥ 20 mL/min/1.73 m² (by CKD-EPI formula, see Section 8.1.2.2)
AND
 - (b) Urine albumin to creatinine ratio (UACR) ≥ 150 and ≤ 5000 mg albumin/g creatinine, based on a single first morning void spot urine sample at screening.

Medical Treatment

- 3 No current or prior (within 1 month of screening) medical treatment with an SGLT2i or any FDC with SGLT2i (such as SGLT2i + metformin).
- 4 If ACEi and/or ARB and/or MRA are prescribed, the dose must be stable ≥ 4 weeks before screening. Participants who have been deemed unable to tolerate ACEi or ARB therapy due to allergy or complications can be enrolled.
- 5 No current or prior treatment within 6 months prior to screening with cytotoxic therapy, immunosuppressive therapy or other immunotherapy for primary or secondary kidney disease.

Weight

- 6 Body mass index (BMI) ≤ 40 kg/m².

Sex

- 7 Male or female of non-childbearing potential.

Reproduction

- 8 Female participants must have a negative pregnancy test at screening, must not be lactating, and must be of non-childbearing potential, confirmed at screening by fulfilling one of the following criteria:
 - (a) Postmenopausal defined as amenorrhoea for at least 12 months or more following cessation of all exogenous hormonal treatments and FSH and LH levels in the postmenopausal range.

- (b) Documentation of irreversible surgical sterilisation by hysterectomy, bilateral oophorectomy, or bilateral salpingectomy but not tubal ligation.
- 9 Male participants must be surgically sterile, abstinent, or in conjunction with a female sexual partner, using a highly effective method of contraception for the duration of the study (from the time they sign consent) and for 3 months after the last dose of investigational product to prevent any pregnancies. Male study participants must not donate or bank sperm during this same time period (see Section 8.3.8.2).

Methods that can achieve a failure rate of less than 1% per year when used consistently and correctly are considered highly effective birth control methods such as:

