6.3 Measures to Minimise Bias: Randomisation and Blinding

All participants will be centrally assigned to randomised, blinded study intervention using an Interactive Response Technology/Randomisation and Trial Supply Management (IRT/RTSM). Before the study is initiated, the telephone number and call-in directions for the IRT and/or the log in information and directions for the RTSM will be provided to each site.

Participants will be stratified by diabetes (DKD versus non-DM CKD) and baseline eGFR (below or equal versus above 45 mL/min/1.73m²) at the time of randomisation to ensure an approximate balance between treatment arms within each sub-population.

- Stratum 1: DKD participants with eGFR \leq 45 mL/min/1.73m².
- Stratum 2: DKD participants with eGFR $>$ 45 mL/min/1.73m².
- Stratum 3: non-DM CKD participants with eGFR \leq 45 mL/min/1.73m².
- Stratum 4: non-DM CKD participants with eGFR $>$ 45 mL/min/1.73m².

The number of randomised participants in each stratum will be monitored to ensure that the non-DM CKD sub-population is approximately 30 to 50% of the total number of participants randomised in the study.

Study intervention will be dispensed at the study visits summarised in the SoA (Table 1). Returned study intervention should not be re-dispensed to the participants.

The IRT/RTSM will provide to the investigator(s) or pharmacists the kit identification number to be allocated to the participant at the dispensing visit.

Routines for this will be described in the IRT/RTSM user manual that will be provided to each centre.

The randomisation code should not be broken except in medical emergencies when the appropriate management of the participant requires knowledge of the treatment randomisation. The investigator documents and reports the action to AstraZeneca, without revealing the treatment given to participant to the AstraZeneca staff.

AstraZeneca retains the right to break the code for SAEs that are unexpected and are suspected to be causally related to an investigational product and that potentially require expedited reporting to regulatory authorities. Randomisation codes will not be broken for the planned analyses of data until all decisions on the evaluability of the data from each individual participant have been made and documented.

The following personnel will be unblinded as to the exact content of investigational treatments (ie, the randomisation code):

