7 DISCONTINUATION OF STUDY INTERVENTION AND PARTICIPANT DISCONTINUATION/WITHDRAWAL

7.1 Discontinuation of Study Intervention

It may be necessary for a participant to permanently discontinue (definitive discontinuation) study intervention.

An individual participant **may be** discontinued from study intervention in the following situations:

- Participant decision. The participant is at any time free to discontinue treatment, without prejudice to further treatment.
- An AE that, in the opinion of the investigator or AstraZeneca, warrants discontinuation from further dosing.
- Severe non-compliance with the CSP.
- Safety reasons as judged by the investigator and/or sponsor where continued treatment may put participant at undue risk.

An individual participant **will be** discontinued from study intervention in the following situations:

- If BNP is increased > 100% from baseline AND is greater than 200 pg/mL; or if BNP is increased > 100% from baseline AND is greater than 400 pg/mL in a participant with atrial fibrillation.
- If the participant or male participant's partner becomes pregnant during the course of the study, investigational products should be discontinued immediately, and an AZ representative notified.
- Diabetic ketoacidosis: DKA including euglycemic DKA have been reported with use of dapagliflozin. Consider temporary interrupting study treatment if DKA is suspected. The participant should be promptly evaluated. If diabetic ketoacidosis is confirmed, investigational product(s) should be discontinued permanently. If diabetic ketoacidosis is not confirmed, restart of study intervention should be considered (see Section 7.1.1 for details).
- Symptomatic hypotension (defined as systolic BP < 90 mmHg OR diastolic BP < 60 mmHg with symptoms).
- eGFR reduction: investigational study products must be discontinued in case of confirmed eGFR reduction from baseline >50% and/or any confirmed decrease below 15 mL/min/1.73m².

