NB. In case a participant shows an AST **or** ALT $\geq 3 \times$ ULN together with total bilirubin $\geq 2 \times$ ULN please refer to [Appendix E](#) - Actions required in cases of increases in liver biochemistry and evaluation of Hy's Law - for further instructions.

^a Central laboratory for all visits.

^b eGFR will be calculated by the central laboratory analysing the sample, using the CKD-EPI formulae in both ways, based on cystatin C and based on creatinine.

^c Any SARS-CoV-2 test except for antibody tests will be acceptable.

Instructions for the collection and handling of the samples will be provided in the study-specific Laboratory Manual.

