3.2.1.3 Serum Analysis of Creatinine and Cystatin C (eGFR)

Estimated GFR is another measure that is considered as a standard for assessment of kidney function. Estimated GFR is calculated based on serum creatinine values using the widely validated and accepted CKD-EPI equation ([Levey et al, 2009](#)). Blood samples for estimation of serum creatinine (clinical chemistry) are collected at various time points during the course of the study as shown in the SoA in [Appendix A: Schedule of Activities](#).

Estimated GFR, using serum creatinine, is calculated as follows:

- $eGFR \text{ (mL/min/1.73 m}^2\text{)} = 141 \times \min(\text{SCr}/\kappa, 1)^\alpha \times \max(\text{SCr}/\kappa, 1)^{-1.209} \times 0.993^{\text{Age}} \times (1.018 \text{ if female}) \times (1.159 \text{ if Black})$

Where SCr = serum creatinine (in mg/dL), κ is 0.7 for females and 0.9 for males, α is -0.329 for females and -0.411 for males, min indicates the minimum of SCr/ κ or 1, and max indicates the maximum of SCr/ κ or 1.

Alternatively, serum cystatin C provides GFR estimates that are nearly as accurate as serum creatinine adjusted for age, sex, and race thus providing an alternative GFR estimate that is not linked to muscle mass ([Scholtes et al, 2020](#), [Stevens et al, 2008](#)). Blood samples will be collected for measurement of cystatin C, at specified time points as shown in the SoA in [Appendix A: Schedule of Activities](#).

Estimated GFR, using cystatin C, is calculated as follows:

- $eGFR = 133 \times \min(\text{S}_{\text{cys}}/0.8, 1)^{-0.499} \times \max(\text{S}_{\text{cys}}/0.8, 1)^{-1.328} \times 0.996^{\text{Age}} \times 0.932 \text{ [if female]}$

Where S_{cys} is standardized serum cystatin C (in mg/L), min indicates the minimum of $\text{S}_{\text{cys}}/0.8$ or 1, max indicates the maximum of $\text{S}_{\text{cys}}/0.8$ or 1, and age = years.

Estimated GFR calculations using the CKD-EPI formulae (in both ways, based on cystatin C and based on creatinine) will be performed by the central laboratory.

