4.7 Demographic and Other Baseline Characteristics

Age will be taken from the demographics form in the eCRF.

Demographic and other baseline characteristics will be listed for all participants and summarised for the FAS as:

- Demographics (age [years], age group [≥ 18 -<50, ≥ 50 -<65, ≥ 65 -<85, and ≥ 85 years], sex, race (if collected), country and ethnicity)
- Participant characteristics at baseline (height [cm], weight [kg], weight group [< 40 , ≥ 40 -<75, ≥ 75 -<90, ≥ 90 -<120, and ≥ 120 kg], body mass index [BMI], BMI group [Underweight (< 18.5 kg/m²), Normal weight (≥ 18.5 - < 25.0 kg/m²), Overweight (≥ 25.0 - < 30.0 kg/m²), Obese (≥ 30.0 kg/m²)], family history of premature cardiovascular disease [Y/N], and substance use [nicotine, alcohol, caffeine and drugs])
- Baseline disease characteristics:
 - T2DM diagnosis [Y/N] and T2DM duration [years] from medical history form in the eCRF
 - Derived CKD stage (eGFR category) [Stage 2 (60-89 mL/min/1.73m²)/Stage 3a (45-59 mL/min/1.73m²)/Stage 3b (30-44 mL/min/1.73m²)/Stage 4 (15-29 mL/min/1.73m²)/Stage 5 (< 15 mL/min/1.73m²)], eGFR (mL/min/1.73m²), albuminuria [defined as 150-5000 mg albumin/g creatinine, with a further categorisation of 'moderate albuminuria' for 150-300 mg albumin/g creatinine and

‘severe albuminuria’ for >300-5000 mg albumin/g creatinine; count and percentage of participants meeting criteria], UACR (mg/g)

- CKD diagnosis, including primary renal diagnosis [Cystic kidney disease, Diabetic nephropathy, Ischaemic/Hypertensive nephropathy, Chronic glomerulonephritis, Renal artery stenosis, Chronic pyelonephritis (infectious), Chronic interstitial nephritis, Obstructive nephropathy, Unknown, Other (Specify)] and chronic glomerulonephritis type [IgA nephropathy, Focal segmental glomerulosclerosis (FSGS), Membranous nephropathy, Minimal change (which is part of exclusion criteria 1), Lupus nephritis, Other primary or secondary glomerulonephritis (Specify)] from CKD diagnosis form in the eCRF
- Angiotensin-converting enzyme inhibitor (ACEi) history [Y/N]
- Angiotensin receptor blocker (ARB) history [Y/N]
- Mineralocorticoid receptor agonist (MRA) history [Y/N]

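### The creatinine eGFR equation has exponent -0.209 in Protocol 8.1.2.2 and -1.209 in SAP 3.2.1.3, and the protocol version does not fit the protocol's own eGFR limits

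*Protocol*

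**What the plan says.** Both documents define creatinine-based eGFR as 141 × min(SCr/κ, 1)^α × max(SCr/κ, 1)^e × an age term × sex and race factors. They agree on 141, κ (0.7 for women, 0.9 for men), α (-0.329 and -0.411), 0.993, 1.018 and 1.159. The cystatin C equation is also the same in both.

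The exponent e differs. Protocol 8.1.2.2 prints "\max(\text{SCr}/\kappa, 1)^{-0.209" and SAP 3.2.1.3 prints "\max(\text{SCr}/\kappa, 1)^{-1.209". In the protocol line the age term has also lost its power sign; the SAP has 0.993 raised to Age.

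The protocol relies on this quantity in several places:

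- **Eligibility.** Inclusion criterion 2(a) requires eGFR of at least 20 and gives the source as "by CKD-EPI formula, see Section 8.1.2.2".
- **Stratification.** Section 6.3 stratifies on "baseline eGFR (below or equal versus above 45 mL/min/1.73m²".
- **Discontinuation.** Section 7.1 acts on a "confirmed eGFR reduction from baseline >50% and/or any confirmed decrease below 15".
- **Endpoints.** Four changes in eGFR are secondary endpoints.

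On who calculates, Protocol 8.1.2.2 says that the estimates "in both ways, based on cystatin C and based on creatinine) will be performed by the central laboratory". The footnote to Protocol Table 5 repeats this: "eGFR will be calculated by the central laboratory analysing the sample, using the CKD-EPI formulae in both ways".

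**The concern.** One equation appears with two exponents that differ by a whole unit, and SAP 4.15, which sets out departures from the protocol, does not mention it. The version in the section that the eligibility criterion cites is the one that looks out of scale. With an exponent near -0.2, eGFR hardly responds to creatinine, so limits at 45, 20 and 15 and a halving from baseline would correspond to creatinine values that do not occur.

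If the laboratory, or whoever supplied the eGFR value for IRT stratification, followed the protocol line, the effects would reach eligibility, the stratum (also a model term in the primary analysis), the discontinuation check and all four eGFR endpoints.

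**Working it through.** **Inputs.** All constants are as printed in Protocol 8.1.2.2 and SAP 3.2.1.3. The limits come from Protocol 5.1, 6.3 and 7.1, the CKD stages from SAP 4.7 and the creatinine flags from SAP Appendix C. Three assumptions are mine: age is read as a power in both versions, the race factor is left out, and 10 mg/dL is taken as a realistic upper limit for serum creatinine.

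**Formula for SCr above κ.** eGFR = 141 × (SCr/κ)^e × 0.993^Age × (1.018 if female).

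**Man aged 60.** 0.993^60 = 0.656, so the multiplier is 141 × 0.656 = 92.5. At SCr 2.0, SCr/κ = 2.0/0.9 = 2.22.
- e = -0.209: 92.5 × 2.22^-0.209 = 78.3
- e = -1.209: 92.5 × 2.22^-1.209 = 35.2

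| SCr (mg/dL) | eGFR, e = -0.209 | eGFR, e = -1.209 |
|---|---|---|
| 2 | 78.3 | 35.2 |
| 3 | 71.9 | 21.6 |
| 4 | 67.7 | 15.2 |
| 10 | 55.9 | 5.0 |

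**Creatinine at each limit.** Inverting, SCr = κ × (target / multiplier)^(1/e). For the man of 60:

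| eGFR | Use in the documents | SCr, e = -0.209 | SCr, e = -1.209 |
|---|---|---|---|
| 45 | stratification | 28.3 | 1.63 |
| 29 | upper end of "Stage 4 (15-29 mL/min/1.73m²" range | 231.6 | 2.3 |
| 20 | eligibility | 1370 | 3.19 |
| 15 | discontinuation | 5427 | 4.05 |

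For a woman of 60, the values at 45, 20 and 15 are 24.0, 1161 and 4597 mg/dL with -0.209, and 1.29, 2.52 and 3.20 with -1.209.

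**Most favourable case tried for the protocol line: woman aged 100.** eGFR 20 still needs 303 mg/dL and eGFR 15 needs 1198. The limit of 45 is softer: she reaches it at 6.2 mg/dL. With SCr capped at 10 mg/dL, 45 becomes reachable from about age 86 in women and 91 in men.

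**Relative falls.** These do not depend on age or sex once SCr is above κ.
- Rise in creatinine that halves eGFR: 2^(1/0.209) = 27.6-fold, against 2^(1/1.209) = 1.77-fold. For the cystatin C line in the same protocol section (exponent -1.328) it is 2^(1/1.328) = 1.69-fold.
- Fall when creatinine doubles (a flag in SAP Appendix C): 1 - 2^-0.209 = 13.5%, against 1 - 2^-1.209 = 56.7%.
- Fall at a 1.5-fold rise (the other flag): 8.1%, against 38.8%.

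**Age term.** Reading the protocol's age term as a product gives 141 × 2.22^-0.209 × 0.993 × 60, or about 7110 at SCr 2.0. The power sign has therefore been lost from that line.

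**The case against.** The strongest reply is that the exponent may not be an authored error. The text was read from PDF by a program, the same line has lost a power sign, and SAP 3.2.1.3 is close to a copy of the protocol section. A line that yields an eGFR in the thousands if taken fully literally could hardly be used unnoticed, and a reader would go to the named CKD-EPI equation. That cannot be excluded, which is why the PDF check comes first. A changed digit is, however, a less common reading fault than a lost superscript, and the other exponents in the section are legible.

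The second reply is that both documents give the calculation to the central laboratory under the CKD-EPI name, nothing says that a site or the IRT computes from the printed line, and the SAP that governs the eGFR analysis already has the version that fits. This stands as a limit on consequence: no harm to the data is shown. It does not remove the contradiction, since neither document shows which exponent was programmed. The Schedule of Activities note on investigator review of laboratory results also refers to eGFR calculations being made, so it does not clearly confine them to the laboratory.

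Two smaller points are fair. The cut of 45 is implausible at most ages rather than unreachable, and the protocol sets no upper age limit. A misprint is also not a planned change of analysis, so its absence from SAP 4.15 shows only that the difference was not declared.

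**Conclusion.** The concern holds. The two documents contradict each other on the exponent, and the documents' own limits show which version is out of line. Under -0.209, eGFR of 20 or 15 and a fall of more than 50% are out of reach at any realistic creatinine, and the two strata at or below 45 would be nearly empty. Under -1.209, the limits of 45, 20 and 15 fall at about 1.6, 3.2 and 4.1 mg/dL for a man of 60.

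These figures rest on reading age as a power and on the digit being as printed in the source PDF, so confidence is medium until the page is checked. Any effect on trial data depends on what the laboratory programmed and on which eGFR value fed the stratification. Even if only the text is wrong, it should be corrected, because an eligibility criterion points to it.

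**What to change.** 1. Check Protocol 8.1.2.2 in the source PDF for the exponent digit and for the power sign on Age.
2. If -0.209 is confirmed, correct it to -1.209 to match SAP 3.2.1.3, the only printed value that is consistent with the documents' eGFR limits. Restore the power sign if it is missing there too.
3. Obtain written confirmation from the central laboratory of the exponent it programmed, and confirm the same for the eGFR value used for IRT stratification. File both with the study documents.
4. If either used -0.209, recalculate eGFR and review eligibility, strata, discontinuation checks and the eGFR endpoints for the participants affected.

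Steps 1 to 3 cost a page check, a one-character correction and written confirmation for the two uses. No eGFR threshold or clinical rule changes.

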8.1.3 Exploratory Variables

8.1.3.1 Electronic Scale Measurement of Body Weight

Home-based body weight monitoring will be performed each morning using the provided digital scales from 2 days before randomisation to end of follow-up (Visit 8) (Table 1 and Section 6.1.2) (also refer to Section 8.2.1).

8.1.3.2 Bioimpedance Spectroscopy

Bioimpedance spectroscopy (BIS) will be performed at the site at the time points specified in the SoA to monitor body fluid volumes (Table 1).

This non-invasive procedure uses skin electrodes to pass a low-level alternating current through the body and measures the impedance to the flow of this current. Tissues such as fat and bone act as insulators; whereas, electrolyte body fluids conduct electrical current and as the fluid increases, impedance to current flow decreases (ie, changes in impedance are inversely proportional to the volume of the extracellular fluid in the body). At low frequencies, cell membranes are non-conductive and current passes only through the extracellular fluid, while at high frequencies, the current passes through cell membranes in addition to the extra- and intracellular fluids.

